Table 4: CRF data collection, source and location.....	Pg.18
Table 5: Schedule of Trial Interventions and Assessments.....	Pg.22

Abbreviations

ACP	Advanced care planning
ADRT	Advance decision to refuse treatment
BHSCT	Belfast Health and Social Care Trust
CORE 34	Clinical Outcomes in Routine Evaluation measure
CRF	Case Report Form
ESKD	End-stage kidney disease
HSCT	Health and Social Care Trust
IST 15	Isaacs Set Test
KDQOL-36™	Kidney Disease Quality of Life instrument
PI	Principal Investigator
RCT	Randomised Clinical Trial
RRT	Renal replacement therapy
SC	Steering committee
SES	Socio-economic status
SHARED	Patient Experience of Shared Decision Making

1. Administrative Information

1.1. Title

Advance care planning with older patients who have end-stage kidney disease: Feasibility of a deferred entry randomised controlled trial incorporating a mixed methods process evaluation.

Trial acronym: ACReDiT

1.2. Trial Registration

ACReDiT (IRAS No 193402)

ClinicalTrials.gov: NCT02631200

1.3. Protocol Version

Version 6.2: September 2016

1.4. Funding

This study is funded by Dunhill Medical Trust. Dunhill Medical Trust has no role in the design of this study and will not have any role during its execution, analyses, interpretation of the data, or decision to submit results.

1.6 Table 3: World Health Organisation Trial Registration Data Set

Data Category	Information
Primary registry and trial identifying number	ClinicalTrials.gov: NCT02631200
Date of registration in primary registry	October 28, 2015
Source(s) of monetary or material support	Dunhill Medical Trust
Primary sponsor	Queen's University Belfast
Contact for public and scientific queries	[name] [name]; [contact]
Public title	Advance Care Planning With Older Patients Who Have End-stage Kidney Disease
Scientific title	Advance Care Planning With Older Patients Who Have End-stage Kidney Disease: Feasibility of a Deferred Entry Randomised Controlled Trial Incorporating a Mixed Methods Process Evaluation
Countries of recruitment	Northern Ireland, United Kingdom
Health condition(s) or problem(s) studied	Advance care planning, kidney failure, chronic
Intervention(s)	Behavioural: Advance care plan
Key inclusion criteria	
 Attending the renal units taking part in the study Receiving renal replacement therapy (RRT) Capacity to understand, retain, and weigh the necessary information and communicate their decisions Identified by their consultant as having worsening symptoms, functional decline, and two or more co-morbidities
Key exclusion criteria	
 Expected to die in the next three months
Study type	Interventional
Date of first enrolment	December 2016
Target sample size	80 (patients and relative/friends)
Recruitment status	Not yet recruiting
Primary outcome(s)	Quality of life: measured by the Kidney Disease Quality of Life instrument - Short Form (KDQOL-36™)
Key secondary outcomes	
 Agreement between the patient and their nominated relative/friend in terms of the patient's preferences: measured by asking the relative/friend to make an independent assessment of the patient's preferences in relation to the key information covered by the ACP intervention, before taking part in the ACP Depression: measured by the Clinical Outcomes in Routine Evaluation measure (CORE 34) The degree to which the patient felt that they had shared in decision-making: measured by the Patient Experience of Shared Decision Making (SHARED) instrument

2. Introduction

2.1. Background and Rationale

The prevalence of moderate to severe chronic kidney disease (defined as stages 3-5 CKD) has been estimated at 6-8.5% amongst adults in the UK¹⁻³ and at over 30% in those aged 75 and over². It is associated with rising risks of hospitalisation, cardiovascular events, cognitive impairment and death⁴. The rapidly growing minority of older patients with CKD who progress to end-stage kidney disease (ESKD) are at even greater risk⁵. However, a substantial proportion of patients and their families do not discuss end-of-life care - including withdrawal of dialysis, ICU admission, involvement of specialist palliative care, cardiopulmonary resuscitation, and place of death – with health professionals^{6,7}. Moreover, the high incidence of impaired cognitive capacity amongst patients with ESKD limits their ability to make informed choices and places additional decision-making burdens on their families^{8,9}. In this situation, advance care planning can be a useful approach to engaging with the patient and their family to help them think through their preferences for care at the end-of-life, leading to better communication between professionals and patients and their families, and improved decision-making should the patient become incapacitated.

Advance care planning (ACP) has been defined as a process of discussion between an individual, their care providers, and often those close to them, about future care.¹⁰ It may lead to an advance statement of preferences; an advance decision to refuse treatment (ADRT); or to the appointment of someone with lasting power of attorney. ACP can be a complex and challenging process for patients, their families and professionals, raising cultural and personal sensitivities around death¹¹; with uptake influenced by a range of social and cultural beliefs, and organisational issues¹². Nevertheless, emerging evidence suggests ACP can reduce rates of hospital admission, increase use of hospice and palliative care, facilitate the delivery of care that is less aggressive, increase patient and family satisfaction, and reduce anxiety and depression in surviving relatives^{11,13-15}. Consequently, in the UK ACP is seen as good practice for those with long-term conditions, or who are at the end of life^{16,17}. It is also recognised as a mark of high quality care in CKD and ESKD¹⁸⁻²⁰.

2.2. Need for a trial

Research into ACP in CKD is limited. A recent systematic review²¹ found some evidence that ACP led to increased well-being and reduced anxiety amongst patients and families. However, most studies

were descriptive, and intervention studies measured a limited set of outcomes. Issues for research included:

- 1) Poor agreement between surrogate decision-makers and patients on end-of-life preferences such as stopping dialysis.
- 2) Difficulties health professionals and patients have in knowing how and when to discuss end-of-life care.
- 3) Patients on dialysis may greatly overestimate their life expectancy.

There is also little available data on cost-effectiveness to guide decision makers in allocating resources for ACP²². Given that ACP is recognised as good practice and yet is a challenging process, research is needed to address issues in relation to implementation, patients' readiness to engage, conservative treatment, withdrawal of dialysis, quality of life, costs, and patient and family outcomes²³.

Benefits and harm:

Participating patients will have the opportunity to complete an ACP with the support of trained facilitators and peer supporters. Evidence suggests that ACP can reduce rates of hospital admission, increase use of hospice and palliative care, facilitate the delivery of care that is less aggressive, and increase patient and family satisfaction. Use of ACP is also associated with reduced anxiety and depression in surviving relatives and there is also evidence that most patients and relatives find taking part in end-of-life research a positive experience, with satisfaction derived from contributing to research that may help others in the future.

National guidance on implementing ACP recommends that peer education of patients should be included, using expert patients¹⁰; and this has been used successfully amongst dialysis patients²⁴. Older patients with ESKD are suitable for inclusion in an evaluation of ACP amongst older adults because they exhibit the mixture of functional decline and co-morbidity typical of frail older people⁵. Implementation and evaluation of ACPs is challenging,²⁵ so intervention processes and research methods should be thoroughly tested before larger scale evaluations are attempted. Therefore, following MRC guidance on the evaluation of complex interventions²⁶, we propose a study to determine the feasibility of a randomised controlled trial (RCT), including a mixed methods process evaluation, to evaluate ACP delivered by professionals (working in partnership with peer supporters), for older patients with ESKD.

2.3. Full Trial Aims and Objectives

The summary objectives for the proposed full trial are stated below so that the relevance of the objectives for the feasibility study can be appreciated.

Full trial objectives:

Primary objective:

- Measure the degree to which implementation of ACP results in desired outcomes for patients with CKD and their families

Secondary objectives:

- Estimate the cost-effectiveness of ACP compared to standard care
- Explain how the process of implementation and the organisational context affect the success or failure of the intervention

2.4. Feasibility Study Aims and Objectives

Aim of the feasibility study: To determine the feasibility of conducting a deferred entry RCT, incorporating a mixed methods process evaluation, to evaluate ACP with patients who have ESKD.

Objectives of the feasibility study:

- Acceptability of the intervention to patients, their relatives, and to health professionals (assessed through interview data)
- Optimal systems for delivering ACP, including the recruitment, training and retention of peer educators (assessed through process mapping, interview data, and reflection by the TMC)
- Recruitment, retention and participation rates (assessed through scrutiny of CRFs)
- Effect sizes that might help inform sample-size estimates for a full trial (assessed by measuring numerical differences between immediate and deferred entry groups in terms of all outcome measures)
- Randomisation procedures and participants' willingness to enter a deferred entry trial (assessed by scrutiny of CRFs and interview data)
- The suitability of a twelve-week deferral period and a nine month process evaluation (assessed by scrutiny of effect sizes and interview data)

- The suitability of survey instruments and outcome measures, including sensitivity of the instruments to detect a change in outcomes (assessed by scrutiny of effect sizes and interview data)
- Time needed to collect and analyse data (assessed by scrutiny of CRFs and researcher records of process study data collection and analysis)
- Estimated resource use and costs of delivering ACP and methods for assessing costs, benefits and cost effectiveness in a full trial (assessed through the range of measures detailed below in section 4.2)

Criteria for progression to a full trial: A protocol for a full trial will be developed if the current study findings indicate that:

- The ACP intervention is acceptable to patients, their relatives/friends and to health professionals
- Peer educators can be recruited, trained, and retained
- ACP can be readily implemented by relevant staff
- Recruitment, participation, and retention rates are likely to be adequate for a full trial
- The instruments are not excessively burdensome to patients or data collectors, and show acceptable reliability and validity
- An economic evaluation is feasible

3. Methods: Design, setting, participants, interventions and outcomes

3.1. Trial Design

Patients and their nominated relative/friends will be recruited to a deferred entry RCT. A traditional RCT could be unethical as ACP issues would be raised but not followed through with patients in the control group. Consequently, this study incorporates a deferred entry trial, where participants are randomised either to an intervention group or a deferred entry control group, as recommended in guidance published by the Medical Research Council and the National Institute of Health Research (NIHR)²⁷. Participants in the deferred entry group have outcomes measured contemporaneously with the immediate entry group but receive the intervention only after trial data collection for the immediate entry group is complete²⁸. Patients, their nominated relative/friends and staff participants will be recruited into the process evaluation, which will last for 12 months from enrolment in the study. This will be underpinned by realist evaluation methodology²⁹, and use qualitative and observational methods, to evaluate issues influencing the success of implementation³⁰⁻³².

3.2. Study Setting

Two sites: the Regional Nephrology Unit at Belfast City Hospital, Belfast Health and Social Care Trust (BHSCT) and the Renal Unit at Antrim Area Hospital, Northern HSCT.

3.3. Eligibility Criteria

Eligible patients will be randomised in equal proportions between the immediate and deferred entry groups.

Patient's eligibility criteria:

- English speaking
- Attending the renal units above
- Aged 65 years or more; with ESKD and receiving RRT

- Capacity to understand, retain, and weigh the necessary information in English and communicate their decisions¹⁰
- Identified by their consultant as having either worsening symptoms, functional decline, or two or more co-morbidities
- Not expected to die in the next three months

Relative/friend eligibility criteria:

- Aged 18 years or older
- Ability to read, write, and speak English
- Identified by the patient as their nominated relative/friend and willing to represent the patient's wishes should they lose decision-making capacity

3.4. Sample size

Forty patient-relative/friend dyads will be recruited onto the trial. Assuming 25% attrition⁴⁴, this sample size is thought to provide sufficient numbers to allow feasibility to be estimated, and to offset the bias in estimates of effect size produced by very small samples^{45,46}.

3.5 Sampling and recruitment

Patients who are already attending the renal units (the Regional Nephrology Unit at Belfast City Hospital, Belfast Health and Social Care Trust (BHSCT) and the Renal Unit at Antrim Area Hospital, Northern HSCT) will be recruited into the study (see below).

Sampling

The sampling frame will be the sampling list of patients obtained from interrogation of the electronic record who appear to meet Stage 1 eligibility criteria as set out in the CRF i.e.

- Attending one of the participating renal units
- Aged 65 or more
- Receiving RRT

The PDRF will split the list by renal unit, and then number patients in an excel file. The two lists of numbers will be sent to [name], who will randomly select 60 numbers from the BCH list and 20 from the AAH list, and then send these numbers back to the PDRF. These numbers will be matched with the sampling list to identify the first 80 patients to be approached to take part.

These patients will be allocated a study ID number by the PDRF, who will also add the study ID to a CRF and print this out.

The PDRF will populate the first page of each CRF (sections 1 and 2) and then pass the CRFs to the ACP nurses in the renal units.

Patient recruitment to the RCT

- Patient screened for stage-one eligibility by the QUB research team (PDRF) (CRF Section 2).
 - Patient may be screened out.
- Patient screened for stage-two eligibility by the ACP Nurse (ACPN) and the patient's consultant (CRF Section 3).
 - Patient may be screened out. CRF passed to the research team.
- ACPN and consultant decide who will make the first approach to the eligible patient.
- ACPN and/or consultant approach the patient to see if they will consider participation (CRF Section 4).
 - Patient may refuse to participate. CRF passed to the research team.
- Patient expresses interest in the study. Given patient and relative information packs and opportunity to discuss the study.
- 2-7 days later, the ACPN follows up with the patient to see if the patient would like to take part (CRF Section 5).
 - Patient refuses to participate. CRF passed to the research team.
- Patient agrees to participate.
 - ACPN checks to see if the patient would like to involve an expert patient in the ACP process (at the ACP discussion, through telephone support, or both).
- Patient and ACPN sign the consent form.
- Consent form passed to the research team
- ACPN checks whether the patient will involve a relative or friend in the ACP process (CRF Section 6a).
 - Patient will not involve a relative/friend. CRF passed to the research team.
- Patient may not yet have decided to involve a relative or friend in the ACP process.
 - ACPN encourages them to speak with a friend or relative and follows up with the patient in the next few days.
- After 3 days/next dialysis session ACPN checks whether the patient will involve a relative or friend in the ACP process (attending the ACP meeting, nominated on the ACP form, or both) (CRF Section 6b).
 - CRF passed to the research team.

- ACP not implemented until baseline data collection, randomisation, and recruitment of relative/friend to the research are completed.

Relative recruitment to the RCT

The initial approach to the relative/friend will be through the patient giving them a 'Relative information pack.' This will make clear that they can act as the patient's nominated relative/friend and decide not take part in the research if they wish.

The relative/friend information will contain the following request:

'If you decide to take part in the research, please do not discuss the details of their plan with the patient until the research starts. This is because we want to see if having an advance care plan makes a difference to the way you discuss these issues together.'

The relative/friend will be invited to express an interest in the research by contacting the research team directly using a dedicated phone number or email address, or a form and reply-paid envelope (CRF Section 8).

If the relative/friend responds to the invitation, the research team will discuss the trial with them and, if they decide to proceed, post or email a consent form to them.

If the patient has indicated that the relative/friend intends to be involved in the ACP process but the relative/friend has not contacted the research team to express an interest in the research, we will send one reminder to the relative/friend through the patient, asking them to consider also taking part in the research.

If they do not respond to this, we will assume they do not wish to take part in the research.

If the relative/friend consents to take part, we will inform them of which group the patient has been randomised to and proceed with data collection accordingly.

We will also ascertain whether they intend to be present for the ACP discussion and inform the ACPN accordingly.

Baseline data collection

Prior to randomisation, recruited patients will be asked to cooperate with baseline data collection, which will include socio-economic status, education, CKD stage, co-morbidities and time since beginning RRT^{38,39} (CRF Sections 8-14). We will collect the following data:

Table 4: CRF data collection, source and location

Data	Data source	Data collector	When and where
GP name, address, telephone	Electronic record	Research Fellow	Trust premises
Patient demographic data	Electronic record	Research Fellow	Trust premises
CKD and RRT status	Electronic record	Research Fellow	Trust premises
List and number of co-morbidities	Electronic record	Research Fellow	Trust premises
Educational level	Patient	Research Fellow	During dialysis
Socio-economic status	Patient	Research Fellow	During dialysis
IST 15 CORE 34 KDQOL-36™ SHARED	Patient	Research Fellow	During dialysis

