3.6. Randomisation

Patients will be randomised once baseline data collection is complete. The randomisation sequence will use blocks of random sizes (from 2 to 8 which will be unknown to the research team members involved in recruitment) to prevent the research team from predicting the randomisation sequence. The allocations will be concealed using sequentially numbered, opaque, sealed envelopes. These envelopes will be opened sequentially after obtaining all patients' consent and, their names and other details have been written on the appropriate envelope. The use of envelopes and participant allocation will be monitored to ensure that the envelopes are used in the correct sequence.

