3.9. Timeline of Trial Outcome Measures

3.9.a. Immediate Entry Group

Baseline/Time 1: Following enrolment and prior to receiving the intervention, patients randomised to the immediate intervention group will complete the IST 15, CORE 34, and KDQOL-36TM, and SHARED. Their nominated relative/friend will make an independent assessment of the patient's ACP preferences before the patient receives the information booklet. Subsequently, the patient and (if the patient wishes) the relative/friend will participate in the ACP intervention.

Time 2: At two weeks following the intervention, the patient will complete the CORE 34 and SHARED, and review their ACP. The nominated relative/friend will make a second independent assessment of the patient's preferences.

Time 3: At 12 weeks the patient will again complete CORE 34, KDQOL-36™, and SHARED and both patient and relative/friend will review the ACP and make any desired changes.

3.9.b. Deferred Entry Group

Patients (and their nominated relative/friends) randomised to the deferred entry group will have outcomes measured contemporaneously with the immediate entry group but receive the intervention only after they have completed three sets of data i.e. at 12 weeks following entry to the trial. At 24 weeks the deferred entry group patients will again complete CORE 34, KDQOL-36™, and SHARED and both patient and relative/friend will review the ACP and make any desired changes. The deferred entry group may have more than one ACP review with the ACPN, however data will only be collected from this group at the final review.

Table 5: Schedule of Trial Interventions and Assessments

Time points	Immediate entry		Deferred entry	
	Patient *	Relative	Patient*	Relative/friend
t₁ baseline	IST 15 CORE 34 KDQOL-36™ SHARED	ACP agreement questionnaire	IST 15 CORE 34 KDQOL-36™ SHARED	
	ACP intervention	ACP intervention		
2/52	ACP 1 st review CORE 34 SHARED	ACP agreement questionnaire (before review) ACP review**	CORE 34 SHARED	
	CORE 34 KDQOL-36™ SHARED ACP 2 nd review	ACP agreement questionnaire (before review) ACP review**	CORE 34 KDQOL-36™ SHARED	ACP agreement questionnaire
24/52			ACP intervention	ACP intervention
			ACP review**	ACP agreement questionnaire (before

		CORE 34 KDQOL-36™ SHARED	review) ACP review**

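### The relative/friend is told the patient's allocation before any relative data are collected, and nothing requires the relative's consent before randomisation, so the agreement outcome starts unblinded and its dyads could differ by arm

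*Combined protocol and SAP*

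**What the plan says.** Four parts of the protocol bear on the order of events.

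- **Trigger for randomisation.** Section 3.5 states: "Prior to randomisation, recruited patients will be asked to cooperate with baseline data collection". Table 4 lists the electronic record and the patient as the only sources; it has no relative item. Section 3.6 adds: "Patients will be randomised once baseline data collection is complete". The consent it requires before envelopes are opened is the patients' consent.
- **Relative recruitment.** The relative is reached by way of the patient: "The initial approach to the relative/friend will be through the patient giving them a" pack of information. For a relative who stays silent, "we will send one reminder to the relative/friend through the patient". The team's next step is then set out: "If the relative/friend consents to take part, we will inform them of which group the patient has been randomised to and proceed with data collection".
- **What relative recruitment must precede.** Section 3.5 ties it to delivery of the intervention: "ACP not implemented until baseline data collection, randomisation, and recruitment of relative/friend to the research are completed". It sets no order between relative recruitment and randomisation.
- **First agreement assessment.** For the immediate arm, section 3.9.a says: "Their nominated relative/friend will make an independent assessment of the patient's ACP preferences before the patient receives the information booklet". For the deferred arm, section 3.9.b has patients and relatives measured at the same times as the immediate arm, with three sets of data before the intervention. Table 5, however, leaves the deferred-arm relative cells empty at baseline and 2 weeks and shows the first agreement questionnaire at 12 weeks.

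**The concern.** The relative is the assessor for the agreement outcome. Randomisation protects a comparison when entry to the sample and the baseline value are both settled before allocation is known. For the patient-reported scales that holds. For agreement the protocol guarantees neither.

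Two separate problems follow. First, the relative's opening assessment is made knowing the group. A relative who knows that the planning meeting is close may think about, or raise, the patient's preferences before filling in the form. Second, if the relative has not consented when the envelope is opened, a patient who has learned the allocation carries the pack or the reminder and may encourage one relative more than another.

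Agreement is listed among the key secondary outcomes in Table 3 and is one of two candidate endpoints for the economic analysis in section 4.2. Section 4.1.b names no between-arm test for it, but section 2.4 calls for differences between the groups on all outcome measures to inform the full trial's sample size. Section 2.4 also makes participation rates and willingness to enter a deferred entry trial feasibility objectives. Relative uptake that partly reflects a known allocation would answer those less cleanly.

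**Working it through.** The point rests on the order of procedures, so the main check sets the sections side by side. The arithmetic afterwards is illustrative.

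**Order of events**

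1. The relative's pack goes out when the patient first expresses interest (3.5), before patient consent. Some relatives may therefore consent before randomisation.
2. The envelope needs patient consent and completed baseline data (3.6). Table 4 shows that those data come only from the record and the patient. Relative consent is not a condition.
3. Disclosure to the relative follows the relative's consent and precedes relative data collection (3.5). Since the relative is told a group already assigned, every relative assessment is made after randomisation and with the allocation disclosed.
4. The timing rule in 3.9.a (before the booklet) places the first assessment before the intervention. It does not place it before allocation or disclosure.
5. One possible counter-sign is that CRF Section 8 is cited both for the relative's expression of interest and as the start of the baseline block (Sections 8-14). An expression of interest is neither consent nor a completed questionnaire, so step 3 stands.

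**The plan's own figures**

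Section 3.4 plans 40 dyads; 40 x 2 = 80 people, which matches Table 3. With 25% attrition, 40 x 0.75 = 30 dyads, or 15 per arm at equal allocation. No relative uptake rate is given, so the size of any selection cannot be derived.

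**Illustration with assumed uptake rates (none is in the protocol)**

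Take n = 20 patients per arm and uptake p1 and p2.

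- Dyads per arm = 20 x p.
- Power to detect the difference (two-sided 0.05) = Phi{[|p1 - p2| - 1.96 sqrt(2 pbar(1 - pbar)/n)] / sqrt[(p1(1 - p1) + p2(1 - p2))/n]}, where pbar is the mean of p1 and p2.
- If willingness to join has correlation rho with agreement, the mean of those who join shifts by rho x phi(c)/p SD, where c = Phi^-1(1 - p). The bias is the difference between arms in this shift.
- phi(c)/p is 0.195 at p = 0.9, 0.350 at 0.8, 0.424 at 0.75, 0.644 at 0.6 and 0.798 at 0.5.

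| Assumed uptake | Dyads | Power to detect | Bias, rho = 0.2 | Bias, rho = 0.5 |
|---|---|---|---|---|
| 90% v 75% | 18 v 15 | 23% | 0.2 x 0.229 = 0.05 SD | 0.5 x 0.229 = 0.11 SD |
| 90% v 60% | 18 v 12 | 60% | 0.2 x 0.449 = 0.09 SD | 0.5 x 0.449 = 0.22 SD |
| 80% v 50% | 16 v 10 | 51% | 0.2 x 0.448 = 0.09 SD | 0.5 x 0.448 = 0.22 SD |

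At 15 dyads per arm the 95% half-width for a standardised difference is 1.96 x sqrt(2/15) = 0.72 SD. Any such bias would sit well inside the sampling error, and an uptake imbalance could easily go unnoticed. If uptake does not depend on allocation, this bias is zero and only the unblinded first assessment remains.

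The illustration counts patients. Section 3.4 counts dyads, so with incomplete uptake more than 40 patients would be needed to reach 40 dyads.

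**The case against.** The strongest reply is that selection by arm is conjecture. Packs go out before randomisation, and the nurse checks on the relative's involvement at patient consent and again within days. The team reveals the group only after the relative consents, so its own disclosure cannot sway that consent. Relatives are also asked not to discuss the plan with the patient until the research starts. All of this stands. A reader might infer that relatives are always recruited after randomisation, or that being told of a 12-week wait makes them decline; the protocol supports neither. Arm-dependent uptake can arise only through a patient who knows the allocation.

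A second reply is that the trial is open-label anyway. That is true of later assessments, but the first could be made without knowledge of the group.

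A third is that, on Table 5, the deferred arm has no baseline agreement value for allocation to distort. A reader might infer two baselines that differ by arm. As tabulated there is only one, so no baseline-adjusted comparison of agreement is possible. That does not remove the concern; it adds a conflict with 3.9.b. The table's layout should be checked in the formatted protocol, because a shifted cell would change this reading.

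Finally, this is a feasibility study, section 2.4 does not ask for participation rates by arm, and reporting consent timing might be thought enough. Reporting would show the extent, but with 20 patients per arm it could not reliably rule out an imbalance.

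**Conclusion.** The concern holds in a limited form. What is documented is the sequence: randomisation does not wait for the relative, and the relative learns the group before giving any data. A difference between arms in which dyads exist is possible but not documented, and its size is unknown. The illustrative bias of about 0.05 to 0.22 SD depends wholly on assumed uptake rates and correlations.

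The effect is confined to agreement, any cost-effectiveness result that uses it as the endpoint, and relative participation rates. A reader might extend it to KDQOL-36, CORE 34 or SHARED; sections 3.5 and 3.6 do not support that, because those baselines are collected before randomisation. The practical consequence is a less trustworthy agreement effect size for planning the full trial. The change is worth making because it is cheap and removes a route to bias, not because harm has been shown.

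**What to change.** 1. In sections 3.5 and 3.6, for patients who nominate a relative, open the envelope only after that relative has consented, declined, or not replied to the single reminder by a fixed deadline. Section 3.5 sets no time limit on the reply at present; without one, randomisation could be held open indefinitely.
2. Tell the patient and the relative the allocation only after any first agreement questionnaire is complete, and remove disclosure as a step before relative data collection.
3. Reconcile Table 5 with section 3.9.b on deferred-arm relative data. If a baseline is intended in both arms, collect it before the envelope is opened and amend Table 5.
4. Report relative consent by arm, with its timing against randomisation.

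Sample size does not change. The costs are revised wording, a short delay to some randomisations, and patient baseline scores that are slightly older at randomisation. The immediate arm should lose little or no time, because section 3.5 already holds the intervention until relative recruitment is complete. If Table 5 is amended, the deferred arm gains one relative questionnaire, which could itself prompt discussion of preferences among controls; that should be weighed when step 3 is settled.
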